Endpoints:	
Primary Endpoint:
 
 • PROMIS® scores of pain intensity and pain interference at 7 days 
Secondary Endpoints:
 
 • PROMIS® scores of pain intensity and interference at 4 weeks • NIH LURN SI-10 scores at 7 days • NIH LURN SI-10 scores at 4 weeks • Composite healthcare utilization metric within 30 days 
 ◦ Hospitalization and ICU care ◦ Unplanned hospitalization ◦ Emergency department visit ◦ Ambulatory encounter: Clinic visit ◦ Ambulatory encounter: Phone call or message • Abnormal imaging findings within 60 days • Stone-free rates within 60 days 
Exploratory Endpoints:
 
 • Number of days taken off work by patient • Number of days taken off work by caregiver • Ecological Momentary Assessments (EMA) measured via daily text message for 10 days 
 ◦ Daily visual analog scale pain survey score ◦ PROMIS® daily ability to participate in social roles and activities score • Composite score difference between Winratio and Desirability Of Outcome Ranking (DOOR) • Number of patients receiving opioid prescriptions • ICIQ-S Treatment Satisfaction scores at 7 days • ICIQ-S Treatment Satisfaction scores at 4 weeks
Study Population:	224 patients, any gender, age ≥18 years, in the State of Michigan
Phase:	Not applicable
Description of Sites/Facilities	Multi-center study of 6 urology practices within the Michigan Urological Surgery Improvement Collaborative (MUSIC) with University of Michigan as the coordinating center.
Enrolling Participants:	
Description of Study Intervention:	Insertion of ureteral stent at the end of ureteroscopy for stone disease. Study arms will consist of either silicone (Coloplast Imajin Hydro) ureteral

stent vs. non-silicone (Polyurethane/Percuflex) ureteral stent (any manufacturer).
Study Duration: 30 months (3 months pre-enrollment and set up; 24 months patient enrollment; 3 months study close and analysis).
Participant Duration: 2 months

Section 3: STATEMENT OF COMPLIANCE

The study will be carried out in accordance with United States (US) Code of Federal Regulations (CFR) applicable to clinical studies (45 CFR Part 46, 21 CFR Part 50, 21 CFR Part 56, and/or 21 CFR Part 812)

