 - Silicone stent placement will be associated with significantly improved NIH LURN SI-10 scores from baseline at 7 days compared to non-silicone stent placement.

- Silicone stent placement will be associated with equivalent difference in NIH LURN SI-10 scores from baseline at 4 weeks compared to non-silicone stent placement.
- Silicone stent placement will be associated with improved composite healthcare utilization metric within 30 days compared to non-silicone stent placement.
 - Hospitalization and ICU care
 - Unplanned hospitalization
 - Emergency department visit
 - Ambulatory encounter: Clinic visit
 - Ambulatory encounter: Phone call or EMR message
- Silicone stent placement will be associated with equivalent abnormal imaging findings within 60 days compared to non-silicone stent placement.
 - New/worsening hydronephrosis
- Silicone stent placement will be associated with equivalent stone-free rates within 60 days compared to non-silicone stent placement.
- Tertiary/Exploratory Endpoint(s):
 - Silicone stent placement will be associated with significantly improved Ecological Momentary Assessment (EMA) scores measured via daily text message for 10 days compared to non-silicone stent placement.
 - Daily visual analog scale survey for pain
 - PROMIS® daily ability to participate in social roles and activities score
 - Silicone stent placement will be associated with significantly less number of days taken off work by patient.
 - Silicone stent placement will be associated with significantly less number of days taken off work by caregiver.
 - Silicone stent placement will be associated with significantly improved composite healthcare utilization metric within 30 days compared to non-silicone stent placement using Desirability of Outcome Rating (DOOR) method
 - The WinRatio and DOOR composite healthcare utilization metric ratios' sizes and directions will be compared.
 - Silicone stent placement will be associated with significantly less number of opioid prescriptions received.
 - Silicone stent placement will be associated with significantly improved ICIQ-S scores at 7 days compared to non-silicone stent placement.
 - Silicone stent placement will be associated with significantly improved ICIQ-S scores at 4 weeks compared to non-silicone stent placement.

Section 6: PATIENT ELIGIBILITY

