The primary endpoints of the study are PROMIS® pain intensity and PROMIS® pain interference t-scores. Each endpoint will be analyzed separately using an ANCOVA model for each. Using the MITT population for analysis, the t-score of the PROMIS® outcome at 7 days post-URS will be the dependent variable and treatment arm and pre-treatment (baseline) PROMIS t-score will be independent variables. The primary comparison of interest is treatment arm. The baseline adjusted mean pain score at 7-days will be reported by arm with the 97.5% confidence interval and a type-3 F-test will test the hypothesis that pain differs between the two treatment groups. Each endpoint modeled will test the effect of treatment arm adjusting for baseline with a type I error of 2.5% for an overall study type I error of 5%.

An analysis in the per-protocol population will be assess the robustness of the effect found in the primary analysis. Additionally, a multivariable model will be considered to account for other patient or surgical variables that may be unbalanced between the arms including timing of stent removal or stone location.

Analysis of the Secondary Endpoints

Additional health-related quality of life endpoints including PROMIS® Pain scores at 4 weeks will be analyzed with similar models described for the primary endpoint. A linear mixed model will be used to compare LURN SI-10 scores at 7 days and 4 weeks between treatment arms. Each analysis will report means with 95% confidence intervals at each time for each arm with a model based type-3 F-test comparing treatment arms.

Healthcare utilization within 30 days of URS will be assessed using a composite endpoint. The composite healthcare utilization metric within 30 days will be a composed score based upon utilization by the patient with each patient assigned a score based upon the highest utilization level that they participate in with levels defined in decreasing order:

5. Hospitalization and ICU care
4. Unplanned hospitalization
3. Emergency department visit
2. Ambulatory encounter: Clinic visit
1. Ambulatory encounter: Phone call or message

We will compare the composite score ranking between the treatment arms using a WinRatio analysis using the unmatched approach.(20) The median composite score for each arm will be reported, along with the WinRatio and associated 95% confidence interval and p-value.

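### The LURN SI-10 model names no baseline score, no arm-by-time term and no time-specific contrast, although Section 5.4 sets separate from-baseline endpoints at 7 days and 4 weeks

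*Combined protocol and SAP*

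**What the plan says.** **Endpoints.** Section 5.4 has two LURN SI-10 entries among the secondary endpoints. The first is "Silicone stent placement will be associated with significantly improved NIH LURN SI-10 scores from baseline at 7 days compared to non-silicone stent placement". The second is "Silicone stent placement will be associated with equivalent difference in NIH LURN SI-10 scores from baseline at 4 weeks compared to non-silicone stent placement". Both refer to baseline, and they expect different results. The synopsis also lists the two times separately but mentions no baseline; its first entry reads only "NIH LURN SI-10 scores at 7 days".

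**Analysis.** Under the secondary endpoints, Section 11.4 says: "A linear mixed model will be used to compare LURN SI-10 scores at 7 days and 4 weeks between treatment arms". The next sentence covers all the quality-of-life analyses: "Each analysis will report means with 95% confidence intervals at each time for each arm", followed by "with a model based type-3 F-test comparing treatment arms". For LURN SI-10 it names no baseline covariate, no arm-by-time interaction, no between-arm difference at a given visit and no equivalence margin.

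**Other models in Section 11.4.** The primary PROMIS model takes the pre-treatment score as a covariate. The 4-week PROMIS models are to be similar to it. The EMA model names an arm-by-day interaction, and the ICIQ-S model uses an arm-by-time interaction to look for a difference at either visit.

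**Data.** Section 8.1 and the time and events table in Section 9 schedule the ROCKS PRO questionnaire before surgery, at 7 days and at 4 weeks. The form in Figure 1 contains the LURN SI-10.

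**The concern.** Two endpoints with different expected results need two answers. A single arm p-value from a model of both visits cannot be assigned to 7 days or to 4 weeks. If it comes from the arm main effect, a benefit confined to the first week is averaged with a visit at which the protocol expects none.

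The baseline score is a separate matter. The endpoint is worded relative to baseline and the pre-operative form is scheduled, yet the score is not named in the model. Section 11.2 justifies baseline adjustment of pain by possible imbalance before surgery. The same reason applies to urinary symptoms.

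Relief of lower urinary tract symptoms is one of the benefits of silicone put forward in Section 4.5, and LURN SI-10 is the only listed endpoint that measures such symptoms. At stake are whether a real 7-day benefit is detected and whether the deciding test is fixed before the data are seen.

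**Working it through.** **Inputs from the documents.** Section 11.2: 101 evaluable patients per arm, PROMIS difference 5, SD 10, two-sided alpha 0.025, power 90%, 10% loss, 224 in total.

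**Assumed inputs.** The documents give no effect, SD or correlation for LURN SI-10. I assume a 7-day effect d of 0.4 or 0.5 SD, equal variances, complete data, correlation r between the two visits of 0.3 to 0.7, correlation of baseline with the 7-day score of 0.5, 101 per arm (borrowed from PROMIS) and two-sided alpha 0.05, matching the planned 95% intervals.

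**The plan's own figure.** n per arm = 2(2.2414 + 1.2816)² × (10/5)² = 99.3, so 100 by the normal approximation. The noncentral t gives 90.1% power at 101 per arm. 101 × 1.10 = 111.1, so 112 per arm and 224 in total. The figure reproduces and is not in dispute.

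**7-day contrast without baseline.** Noncentrality = d√(101/2).
- d = 0.5: 3.55, power 94%.
- d = 0.4: 2.84, power 81%.

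**7-day contrast with baseline.** The residual SD becomes √(1 − 0.5²) = 0.866. For d = 0.4 the standardized effect is 0.4/0.866 = 0.462, noncentrality 3.28, power 90%.

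**If the F-test is the arm main effect.** It estimates the mean of the two visit effects. With d at 7 days and 0 at 4 weeks that mean is d/2, and a patient's two-visit mean has SD √((1 + r)/2). The standardized effect is therefore (d/2)/√((1 + r)/2). If half the effect persists at 4 weeks, the mean effect is (d + d/2)/2 = 0.75d.

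**If the F-test is a joint 2-df test** (arm plus arm-by-time), noncentrality = (101/2) × d²/(1 − r²); power is from the noncentral chi-square.

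Power for d = 0.5, against 94% for the 7-day contrast:

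| r | SD of mean | Averaged, no 4-week effect | Averaged, half persists | Joint 2-df, no 4-week effect |
|---|---|---|---|---|
| 0.3 | 0.806 | 59% | 91% | 93% |
| 0.5 | 0.866 | 53% | 86% | 97% |
| 0.7 | 0.922 | 48% | 82% | over 99% |

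For d = 0.4 and no 4-week effect, against 81% for the 7-day contrast, the averaged test has 37% at r = 0.5. The joint test has 76%, 84% and 95% at r = 0.3, 0.5 and 0.7.

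**The case against.** The strongest reply is that the pooled test is inferred. The F-test sentence is generic and also governs the 4-week PROMIS models, so its singular wording does not establish one pooled LURN SI-10 test. Means by arm at each time are natural output of an arm-by-time model, and listing the two times as separate endpoints favours time-specific comparisons. This stands. A reader might infer that the plan commits to a diluted test. The documents do not support that: averaging is the natural reading of one model with one arm test, but it is not written. A 7-day contrast would lose nothing, and a joint test little or nothing. The joint test would still not say at which visit the arms differ.

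On baseline, the preceding sentence gives additional quality-of-life endpoints models similar to the primary one, and LURN SI-10 might be meant to fall under it. That is possible, but LURN SI-10 then gets its own sentence with a different model and no covariate. A reader might also infer that omitting baseline biases the comparison, or that the endpoint is settled as change from baseline. Neither holds. Randomization protects the comparison, so the cost is precision; and the synopsis lists only scores, so the endpoint wording itself is unsettled.

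Finally, the sizes rest on assumed effects and correlations, and a zero 4-week effect is the worst case among non-negative ones. That also stands. Zero is nevertheless the pattern that the equivalence hypothesis in Section 5.4 suggests.

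**Conclusion.** The concern holds as under-specification with a concrete remedy. Section 11.4 does not say which test answers which LURN SI-10 endpoint, and it leaves a scheduled baseline score out of the named model. It specifies arm-by-time terms for two exploratory endpoints but not for this secondary one.

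The precision loss does not depend on how the F-test is read, only on the baseline score being left out: 81% against 90% power at 7 days for d = 0.4, if baseline correlates 0.5 with the outcome. The larger loss, from 94% to 48–59% at d = 0.5, is conditional on the arm main effect being tested and on no effect remaining at 4 weeks. If half the effect persists, the averaged test has 82–91%. All these sizes are illustrative.

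The 4-week endpoint has a further gap: a non-significant F-test cannot show equivalence, and no margin is stated. The change should be made, but this is a secondary endpoint and neither the primary analysis nor the sample size is affected.

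**What to change.** Rewrite the LURN SI-10 part of Section 11.4:

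- Fit the 7-day and 4-week scores in one mixed model with fixed effects for arm, time, arm-by-time, baseline LURN SI-10 and baseline-by-time.
- Name the arm contrast at 7 days as the superiority test for the 7-day endpoint.
- Report the arm difference at 4 weeks separately with its 95% confidence interval. Claim equivalence only against a margin stated in advance; otherwise describe the result as an estimate.
- Do not use an arm test averaged over visits for either endpoint.
- Align the synopsis and Section 5.4. With baseline in the model, the arm difference at a visit is the same whether the outcome is the score or its change from baseline, so either wording can be adopted in both places.

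The cost is about one paragraph of text, the choice of a margin if equivalence is to be claimed, and a matching edit to the endpoint lists. No new data or patients are needed.

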Participants at a given performance site who meet all inclusion/exclusion criteria will be randomized using Randomize.net or a similar randomization methodology as endorsed by the Michigan Institute for Clinical & Health Research (MICHR). Subjects will be randomized to either silicone or non-silicone ureteral stent placement at a 1:1 allocation ratio. Blocked, stratified randomization based upon surgeon classified stone location (renal only versus ureteral), with random block sizes will be used to ensure group balance. Randomization list will be determined separately in strata defined by state the stratification factor/s here. The randomization code will be generated by an independent statistician.

At the time of surgery, if baseline PRO has been completed, prior to placement of the stent, the surgeon will be notified via email/text message and the surgeons operating room staff can reference the MUSIC registry to confirm if the patient should have a silicone vs non-silicone stent based on random allocation by the BLUES study coordinator or another member of the BLUES study team. Only patients who are randomized, remain eligible prior to stent placement, and receive the study treatment will be counted towards the treatment population of 224 participants. These patients will receive PRO questionnaires, via the ROCKS PRO infrastructure, pre-operatively and at 7 days, and 4 weeks after surgery. If the patient is unable to complete the PRO questionnaires through the ROCKS PRO infrastructure, the patient may complete an email survey via REDCap, survey by phone from a BLUES study team member, or paper questionnaires. Patients will also receive text messages which include pain-specific questionnaires to be completed daily for 10 days after surgery. The process of completing the ROCKS PRO questionnaire is

the same, regardless of the patient's participation in the BLUES study. A patient can withdraw or decline participation in BLUES and/or ROCKS PRO at any time.

Section 8: TREATMENT PLAN

Section 8.1: Treatment overview

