An interim analysis for futility is planned after accrual of 112 patients. The study will stop early if it is found that the silicone stent arm has clinically significant worse pain intensity and worse pain interference at 7 days with worse pain defined as 5 or greater t-score points worse pain in the silicone stent arm compared to the non-silicone stent arm after adjusting for baseline. Under the alternative hypothesis for both endpoints simulations of 1000 trials estimates the probability of stopping early is 0%. If we assume that the silicone stent is worse than the non-silicone stent by 5 points simulation of 1000 trials estimates the probability of stopping early is 24.4%.

Section 11: STATISTICAL CONSIDERATIONS

Section 11.1: Statistical Hypotheses

This is a multi-center two-arm stratified, randomized comparative effectiveness study in patients are treated with URS for nephrolithiasis with a planned placement of a stent to assess patient reported quality of life. The primary hypothesis is that the silicone ureteral stent arm will have superior patient reported pain outcomes compared to the non-silicone stent arm. Patients will be stratified by stone location (kidney only / ureteral) and randomized to receive a silicone stent or a non-silicone stent and complete the PROMIS® pain intensity and PROMIS® pain interference surveys prior to surgery and at 7 days after stent placement.

Our formal statistical hypotheses are:

$$H_0: \mu_{ns} = \mu_{ss}, \quad H_1: \mu_{ns} \neq \mu_{ss}$$

where, μ_{ns} = mean PROMIS® pain intensity in non-silicone stent arm at 7 days

μ_{ss} = mean PROMIS® pain intensity in silicone stent arm at 7 days

AND

$$H_0: w_{ns} = w_{ss} \quad H_1: w_{ns} \neq w_{ss}$$

where, w_{ns} = mean PROMIS® pain interference in non-silicone stent arm at 7 days

w_{ss} = mean PROMIS® pain interference in silicone stent arm at 7 days

Section 11.2: Power/Sample Size:

Assume that the correlation of baseline is 0 for purposes of the sample size calculation. If this assumption is violated, the power for each hypothesis will be greater than the stated power.

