Abnormal imaging and stone-free rates will each be summarized as a count with the associated proportion by treatment arm and tested with a chi-square test (or fisher's exact test if event counts are 5 or less.)

Planned Interim Analyses

An interim analysis for futility is planned after accrual of 112 patients. The study will stop early if it is found that the silicon stent arm has clinically significant worse pain intensity and worse pain interference at 7 days with worse pain defined as 5 or greater t-score points worse pain in the silicone stent arm compared to the non-silicone stent arm after adjusting for baseline. Under the alternative hypothesis for both endpoints simulations of 1000 trials estimatas the probability of stopping early is 0%. If we assume that

the silicone stent is worse than the non-silicone stent by 5 points simulation of 1000 trials estimates the probability of stopping early is 24.4%.

Sub-Group Analyses

A sub-group analysis by stone location is planned. Primary and secondary endpoints will be reported for ureteral stones separately from renal stones.

Exploratory Analyses.

The mean (with standard deviation) or median (with interquartile range) days taken off work by patient and separately by caregiver will be compared between treatment arms with a t-test or Wilcoxon rank test if the distribution warrants.

Ecological Momentary Assessments of pain and PROMIS® daily ability to participate in social roles and activities score measured via daily text message will be displayed using spaghetti plots. Each measure will be analyzed with a linear mixed model including fixed effects of treatment arm, day, and the interaction of treatment arm and day. As this is an exploratory endpoint, these models will be explored using several methods to address missing data and model fit.

Each healthcare utilization metric within 30 days of URS will be summarized separately as a count with the associated proportion by treatment arm and tested with a chi-square test (or Fisher's exact test if event counts are 5 or less.)

In an exploratory analysis to create a composite endpoint to be used in future trials we will assess the plausibility of 2 composite measurement plans and analyses of these.

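### The exploratory EMA mixed models leave out the baseline PROMIS pain score and stone location, a small gain in precision that needs no new data

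*Combined protocol and SAP*

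**What the plan says.** Section 11.4 (Exploratory Analyses) gives the EMA analysis in one sentence: both measures are to have a "linear mixed model including fixed effects of treatment arm, day, and the interaction of treatment arm and day". It adds that, because the endpoint is exploratory, "these models will be explored using several methods to address missing data and model fit". No baseline score and no stratification factor is named.

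The EMA data are post-operative only. Section 7 states: "Patients will also receive text messages which include pain-specific questionnaires to be completed daily for 10 days after surgery". Pre-operative pain is nevertheless recorded on another instrument: under Section 11.1, patients "complete the PROMIS® pain intensity and PROMIS® pain interference surveys prior to surgery and at 7 days after stent placement". The primary ANCOVA in Section 11.4 uses that score: "treatment arm and pre-treatment (baseline) PROMIS t-score will be independent variables". Section 11.2 says that a baseline correlation above zero would give more power than the calculation claims.

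Section 5.4 states the EMA hypothesis as one about level: silicone stents will be associated with "significantly improved Ecological Momentary Assessment (EMA) scores measured via daily text message for 10 days". Section 7 makes stone location (renal only or ureteral) the stratification factor for randomisation.

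**The concern.** The plan accepts the case for baseline adjustment in its primary analysis but does not carry it over to the daily pain series, which covers the same domain in the same patients. Whatever part of the between-patient variation in daily pain is predictable from pre-operative pain stays in the error term. Stone location, which the design balances, is also left out.

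The section also does not say which arm contrast will be reported. An arm-by-day term asks whether the gap between arms changes over the 10 days. A constant benefit would leave that term at zero, although the hypothesis in Section 5.4 concerns better scores over the period.

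At stake is the width of the interval for an exploratory comparison, together with some protection against chance baseline imbalance. If replies to the text messages depend on pre-operative pain, conditioning on it also makes the mixed model's missing-at-random assumption more plausible.

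**Working it through.** **The plan's own figure.** Section 11.2 gives no sample size or power for EMA. It does give one for the primary endpoints: difference 5, SD 10, two-sided alpha 0.025, 101 per arm, 90% power. A noncentral t calculation gives 89.8% power at 100 per arm and 90.1% at 101, so the figure reproduces. Allowing for 10% loss, 202 / 0.9 = 224.4 against the stated 224. With baseline adjustment the SD becomes 10 × √(1 − ρ²), and power at 101 per arm rises to 92.8% at ρ = 0.3 and 96.7% at ρ = 0.5. This bears out the plan's remark about extra power.

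**The same argument for the EMA average.** Let R be the correlation between baseline PROMIS pain and a patient's mean EMA score over the 10 days. The documents do not give R, so it is assumed, from 0 (the value that Section 11.2 takes for the primary outcome) to 0.5. Adjustment multiplies the variance of the average arm difference by 1 − R² and its standard error by √(1 − R²).

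| R (assumed) | 1 − R² | Variance reduction | √(1 − R²) | SE reduction |
|---|---|---|---|---|
| 0 | 1.00 | 0% | 1.000 | 0% |
| 0.2 | 0.96 | 4% | 0.980 | about 2% |
| 0.3 | 0.91 | 9% | 0.954 | about 5% |
| 0.4 | 0.84 | 16% | 0.917 | about 8% |
| 0.5 | 0.75 | 25% | 0.866 | about 13% |

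The same factor applies to a single-day arm contrast if the correlation is with that day's score.

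**Which correlation is meant.** Averaging removes day-to-day noise, so a given correlation ρ with daily scores implies a larger R. With within-patient day-to-day correlation r (compound symmetry, also assumed), R² = ρ² / [(1 + 9r)/10]. For ρ = 0.3 and r = 0.5, R² = 0.09 / 0.55 = 0.164, and the SE ratio is √(1 − 0.164), or about 0.915. With r from 0.4 to 0.7, the ratio at ρ = 0.3 runs from 0.897 to 0.936. These figures use a different input from the table and should not be mixed with it.

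**Simulation.** Random-intercept models were fitted with and without baseline (101 per arm, 10 days, r = 0.5, 30 replicates per scenario). The SE ratios for the average arm effect were 1.00, 0.92 and 0.73 at ρ = 0, 0.3 and 0.5; the formula gives 1.000, 0.915 and 0.739.

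**Where there is no gain.** In the same simulations the SE ratio for the linear arm-by-day slope was 1.000. A baseline score is constant within a patient, while the slope is estimated from change within patients.

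**The case against.** The strongest reply is that the plan leaves the model open. Its list of fixed effects is introduced by a word that need not be exhaustive, and the models are to be explored further. Nothing bars a baseline covariate, and no error control or primary conclusion rests on this endpoint. That sets the weight of the point, but the stated scope for exploration is missing data and model fit, so the wording does not supply the adjustment.

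The analogy with the primary ANCOVA is also imperfect. There, a PROMIS score is adjusted for the same score. Here, no pre-operative VAS or social-roles score exists. The covariate is a different instrument, completed before surgery by patients who, under Section 6.2, have no indwelling stent. The correlation could therefore be low, which is why the range starts at zero. For social roles, pain interference is only indirect. This objection stands in full as a limit on the size of the gain.

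A reader might infer that the plan tests the interaction alone. The documents do not say so: the model has an arm term and Section 5.4 states a direction. What is missing is a named contrast. Nor should the day 1-10 average displace the arm-by-day results. Stents come out at the surgeon's discretion (Section 8.1), often 1-3 weeks after placement (Section 4.3), so later EMA days can mix patients with and without a stent and the effect may vary by day.

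A reader might also infer that every randomised patient must have a baseline score. Section 7 is conditional: "At the time of surgery, if baseline PRO has been completed, prior to placement of the stent". It does not say what happens otherwise, and Section 8.1 provides reminders for patients who miss the survey. A rule for missing baseline scores is therefore needed.

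**Conclusion.** The point holds as a minor, optional improvement. The listed EMA model terms omit an available pre-operative pain score and the stratification factor. Including baseline pain would reduce the standard error of the average arm difference by about 0% to 13% for assumed correlations of 0 to 0.5 with the patient's mean EMA score. The true correlation is unknown, and at zero there is no gain. Day-specific arm differences can gain too; a linear arm-by-day slope does not. No figure can be put on the contribution of stone location; the reason to include it is that it stratified the randomisation.

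It would be wrong to read this as bias. Randomisation keeps the unadjusted comparison unbiased apart from missing data, so what may be lost is precision. The sample size and the primary conclusion are unaffected.

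**What to change.** Before the unblinded analysis, amend the EMA paragraph of Section 11.4 as follows:

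- In the daily pain VAS model, add the baseline PROMIS pain intensity T-score and stone location as fixed effects.
- In the social-roles model, baseline pain interference may be added, described as an indirect covariate with a probably smaller gain.
- Keep patients with a missing baseline score in the model, for example by simple baseline imputation that does not use arm or outcome.
- Report the adjusted average arm difference over days 1-10, which matches the claim about level in Section 5.4, alongside the planned arm-by-day results and not in place of them.

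The cost is a few sentences of text. No new data, visits or patients are needed.
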